1.0 Background & Rationale

Every year, 150,000 Americans are hospitalized for complications of liver cirrhosis.² These patients suffer from debilitating symptoms (ascites, gastrointestinal bleeding, infection, and hepatic encephalopathy).³ They also have impairments in physical, cognitive, psychological, and social functions leading to poor quality of life and long-term disability.^{1, 4-7} These impairments contribute to high utilization of health care resources; within 30 days of hospital discharge, 25% of patients are readmitted, and of these readmissions, 20-40% are preventable.⁸⁻¹⁰ This inpatient health care utilization is the largest driver of the \$30 billion spent annually on chronic liver disease.¹¹ These individual and societal burdens of cirrhosis could be improved with existing health care services, behavioral care, rehabilitation services, and community resources; but the current fragmented nature of the health care system does not allow for the necessary coordination to best care for this population.¹²

To address the health care system's lack of care coordination, the Institute of Medicine and Centers for Medicare and Medicaid Services recommend the development of collaborative care models (CCM) in a wide range of clinical settings.^{13, 14} CCMs are intended to provide coordinated, personalized care pragmatically using care coordinators. CCMs have successfully improved care in multiple patient populations, ranging from frail older adults to depression.¹⁵⁻²⁵ In contrast, for patients with cirrhosis, there is a paucity of data to support the benefit of CCM in this medically complex and vulnerable population.²⁶ At Indiana University, researchers have over 20 years of experience in developing, testing, and implementing CCMs successfully for patients living with dementia or depression.^{15, 16} Building on these successes, we have customized the CCM to best meet the unique and complex biopsychosocial needs of patients with cirrhosis: the Cirrhosis Medical Home.

In the Cirrhosis Medical Home, a care coordinator, supported by an interdisciplinary clinical team, will deliver a personalized intervention guided by a set of innovative tools: (i) patient-centered care protocols, (ii) a mobile office, (iii) care coordination support software, and (iv) dynamic feedback measures. The overall goal is to improve quality of life and to reduce acute health care utilization for patients with cirrhosis. In this pilot, randomized trial of 40 patients, we aim to refine our study processes in preparation for a large scale randomized controlled trial evaluating the efficacy of the Cirrhosis Medical Home in improving the quality of life of patients discharged from the hospital with cirrhosis. Additionally, up to 40 caregivers will be enrolled in the trial.

2.0 Objective(s)

- 2.1** The primary objective of this trial is to test the screening and enrollment processes for a randomized controlled trial of the Cirrhosis Medical Home compared to usual care for patients with decompensated cirrhosis and poor quality of life when discharged from the hospital
- 2.2** Secondary objectives are:

- 2.2.1 to assess the data collection process, outcome assessment, and the acceptability of the Cirrhosis Medical Home trial
- 2.2.2 to estimate the effect size of the Cirrhosis Medical Home intervention on quality of life at six months post hospital discharge

3.0 Study Measures

All primary and secondary outcomes measures will be obtained from study participants at baseline and at 3 and 6 months, per the schedule of events. Additionally, MELD and Child-Pugh scores will also be obtained at the 3 and 6 month assessments.

3.1 Primary Outcome (Feasibility) Measures

3.1.1. Enrollment rate: The enrollment rate is the number of patients/caregivers enrolled per month. We will further determine the number of patients/caregivers screened and approached for enrollment. Based on these numbers, we will calculate the proportion of screened patients/caregivers eligible for enrollment, the proportion of eligible patients/caregivers approached, and the proportion of approached patients/caregivers enrolled. Of those not eligible, we will record reasons for ineligibility. Of those eligible, but not approached, we will record reasons. For those approached, but not enrolled, we will record reasons.

3.1.2 Drop-out rate: The drop-out rate is the proportion of enrolled participants (patients and caregivers) who drop out of the study before completion.

3.1.3 Data completion: We will record the completeness of the data collection for enrolled subjects. For those with incomplete data, we will record reasons that data could not be collected.

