3.2 Secondary Outcome Measures

3.2.1. Quality of Life: This outcome will be obtained from the patient only. Patient health-related QOL will be assessed using the Medical Outcome Study Short Form (SF-36).^{40, 48, 49} This scale has eight components (physical functioning, role-physical, bodily pain, general health, vitality, social functioning, role-emotional, and mental health) that are aggregated into a Physical Component Summary (PCS) and a Mental Component Summary (MCS). Changes that differ by 2 or more points on a scale of 0 to 100 are clinically meaningful.⁴⁹

3.2.2 Physical Performance: Physical performance measures will be obtained from the patient only. Physical recovery will be assessed via the Short Physical Performance Battery (SPPB), a validated objective assessment.⁵⁰ The SPPB yields a performance score of 0-12 (0-4 poor, 5-7 intermediate, 8-12 good). A difference of 1 point indicates significant change in function. The SPPB has been validated in patients with decompensated cirrhosis.^{51, 52} Grip strength will also be obtained to calculate the Liver Frailty Index, <https://liverfrailtyindex.ucsf.edu>, which overlaps with the SPPB.

3.2.3 Depression and Anxiety Symptoms: Depression and anxiety symptoms will be obtained from the patient only. The Patient Health Questionnaire-9 (PHQ-9)^{53, 54} and Generalized Anxiety Disorder Scale (GAD-7)^{55, 56} will be used to measure patient mood and anxiety. The PHQ-9 is a nine-item depression scale with a total score from 0 to 27, and the GAD-7 is a seven-item anxiety scale with a total score from 0 to 21. Both of these scales are derived from the Patient Health Questionnaire, have good internal consistency and test-retest reliability as well as convergent, construct, criterion, procedural and factorial validity for the diagnosis of major depression and general anxiety disorder.

3.2.4 Cognitive Assessment: Cognitive assessment will be obtained from the patient only. 3D CAM and PHES are psychometric measures of hepatic encephalopathy. They are quick, simple paper tests that are easily interpreted. They are components of the gold-standard Psychometric Hepatic Encephalopathy Score.⁵⁷⁻⁶⁰

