3.2.5 Caregiver Burden: Caregiver burden will be obtained from the caregiver only. The Zarit Burden Interview-12 (ZBI-12) is a validated instrument that has been utilized in various populations.⁶¹ It has excellent test characteristics when compared with the long form of the ZBI, and it has been used in other studies of cirrhosis.^{4, 62}

3.2.6 Acute Health Care Utilization: Health care utilization will be obtained from the patient only. In addition to patient-reported emergency room and admission data, we will use the Indiana University Health local data warehouse and the larger Indiana Network for Patient Care (INPC) to complement the utilization assessment. INPC is a large health information exchange in Indiana and provides data from all health care systems within the state.⁶³ We will determine the number of emergency room visits and the number of hospitalizations within 6 months of discharge as well as associated diagnoses. As part of this, we will also be tracking admissions specific to COVID-19, due to the large impact the pandemic has had on our healthcare system. We will do that by tracking whether patients are admitted with a COVID-19 diagnosis or die of COVID-19 while enrolled in the study.

3.2.7 CMH Interactions: In patients/caregivers randomized to the Cirrhosis Medical Home, we will record the numbers, timing, and types of interactions with the care coordinator (in-person, phone, video, other forms of communication). We will also record the use of interventions (e.g. care protocols, pharmacologic treatments).

3.2.8 Palliative Care outcomes: Palliative care referrals will be recorded, including presence of a referral order, successful attendance at a palliative care visit, completion of advanced directives, and place of death.

3.3 Other Patient Measures: At baseline, we will measure age, race, gender,

level of education, income, employment, family size and household composition, height, weight, etiology of cirrhosis, liver disease severity (Child-Pugh score,⁶⁴ MELD score⁶⁵), Charlson comorbidity index,⁶⁶ medications, prior health care utilization, and reason for hospital admission.

3.4 Other Caregiver Measures: At baseline, we will measure age, race, gender, location (living with the patient or elsewhere), relationship to patient, and length of time caring for the patient.

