5.0 Study Design

This is a pilot, randomized controlled trial to establish the feasibility of enrollment, data collection, and outcome assessment for a future efficacy trial. Participants will be enrolled and randomized to the Cirrhosis Medical Home or usual care at the time of hospital discharge and will be followed for 6 months.

The goal of this proposal is to establish the feasibility of a randomized controlled trial comparing the Cirrhosis Medical Home to usual care in improving QOL and health care utilization of patients with decompensated cirrhosis and poor QOL. To achieve this goal, we propose a feasibility study in which we will randomize 40 patients to the Cirrhosis Medical Home or usual care, assessing QOL; physical, cognitive, and psychological symptoms; and health care utilization. Figure 1 shows the conceptual model.³⁸ We hypothesize that the Cirrhosis Medical Home will improve QOL through its effects on physical, psychological, and cognitive recovery, and that this improvement in QOL will result in decreased health care utilization.

Figure 1. Cirrhosis Medical Home Conceptual Model

[figure not shown]
In addition, 40 caregivers of people with cirrhosis will be enrolled in the study. They will complete the Zarit Burden Interview-12 (ZBI-12) at baseline, 3 months and 6 months. For those caregivers who care for participants who are randomized into the CMH arm, the caregivers will complete the HABC-M Caregiver assessment during their interactions with the CMH care coordinator. The HABC-M for the Caregiver is not a study outcome but is an assessment that the care coordinator uses to help guide the individualized care plan for the patient.

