11.0 Statistical Considerations

This is a pilot trial for feasibility and effect size estimation. The plan is to enroll 40 total patients and randomize in 1:1 ratio to the Cirrhosis Medical Home and usual care. As a pilot trial, the study is not powered to test efficacy, but is designed to generate preliminary data to support a larger future trial. The sample size of 40, enrolled over 9 months (see study timeline in section 13), will allow for recruitment of approximately one patient/caregiver dyad per week. Data collected from this pilot will be used to provide an estimate of intervention effect, i.e. the difference in the primary outcome measure (SF-36) between intervention and control groups. The pilot data will also provide estimates on variability in the outcome measures in this patient population. The effect and variability estimates from the pilot data will be used to power a large trial. The sample size of 40 will provide 80% probability that the 95% confidence interval for the estimated treatment difference with half-width of 0.7SD will contain the true treatment effect. The pilot sample size of 40 has also been shown to minimize the overall sample size of the pilot and the main trial together with 80% power in the main trial to detect effect sizes in the range of 0.1~0.3SD.⁶⁷

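### Section 3.1.2 pools patients and caregivers into one drop-out rate, which equals patient attrition only if both groups leave at the same rate; report the two separately (minor, cheap improvement)

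*Combined protocol and SAP*

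**What the plan says.** Section 3.1 lists three primary feasibility measures: enrollment rate, drop-out rate and data completion. On the second, 3.1.2 reads: "The drop-out rate is the proportion of enrolled participants (patients and caregivers) who drop out of the study before completion". The available text defines no separate patient or caregiver rate, and Section 11.0 contains no drop-out analysis, target or allowance.

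On numbers, Section 11.0 says "The plan is to enroll 40 total patients and randomize in 1:1 ratio". Section 5.0 says "40 caregivers of people with cirrhosis will be enrolled in the study", whereas Section 1.0 gives 40 caregivers only as a maximum. Section 7.0 (Individualized Care Plan) provides for patients without a participating caregiver, and the key to the Schedule of Events (16.1) requires the caregiver HABC-M only where a caregiver is enrolled.

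On outcomes, Section 3.2.1 says of quality of life (SF-36): "This outcome will be obtained from the patient only". Section 3.2.5 says "Caregiver burden will be obtained from the caregiver only", and Section 5.0 adds for caregivers: "They will complete the Zarit Burden Interview-12 (ZBI-12) at baseline, 3 months and 6 months". Section 11.0 describes the intervention effect to be estimated as "the difference in the primary outcome measure (SF-36) between intervention and control groups" and says that the pilot's effect and variability estimates will be used to power a large trial.

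**The concern.** Patients and caregivers are two populations with different roles in the study. A single proportion across both is a weighted average, and the weight depends on how many caregivers happen to enroll. The same patient attrition can therefore produce different values of a primary outcome, and different patient attrition can produce the same value.

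The pilot is meant to prepare a larger trial of quality of life. For a patient-reported outcome, the retention figure a planner needs is the proportion of patients lost. The outcome as defined does not report it. At stake is whether the headline drop-out figure describes what readers will take it to describe.

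**Working it through.** **The plan's own figure.** The plan states no drop-out rate, so there is none to reproduce. The nearest figure is the precision statement in Section 11.0 (40 patients, 95% interval, half-width 0.7SD, 80% probability). Read as the probability that the half-width is no more than 0.7SD, with all 20 per arm analysed:

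- Half-width at the true SD: t(0.975, 38) × √(2/20) = 0.640SD.
- P(half-width ≤ 0.7SD), from the chi-square distribution of the sample variance on 38 degrees of freedom: 0.810, against the stated 80%.

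That figure uses no drop-out rate, so the definition in 3.1.2 does not affect it.

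**Inputs.** Np = 40 patients (Section 11.0). Nc = 40 caregivers (Section 5.0), with Nc = 20 as an assumed lower case because 40 is elsewhere only a ceiling. The drop-out rates dp (patients) and dc (caregivers) are assumptions throughout.

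**Formula.**

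Pooled rate = (Np·dp + Nc·dc) / (Np + Nc)

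Pooled rate − dp = Nc·(dc − dp) / (Np + Nc)

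If Nc > 0, the difference is zero only when dc = dp. With Nc = 40 it is half the gap between the two rates; with Nc = 20 it is one third (20/60).

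**Results under assumed rates.**

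| Np, Nc | dp | dc | Pooled | Pooled − dp |
|---|---|---|---|---|
| 40, 40 | 30% | 10% | (12+4)/80 = 20% | −10 points |
| 40, 40 | 20% | 30% | (8+12)/80 = 25% | +5 points |
| 40, 40 | 30% | 30% | (12+12)/80 = 30% | 0 |
| 40, 20 | 30% | 10% | (12+2)/60 = 23.3% | −6.7 points |
| 40, 20 | 20% | 30% | (8+6)/60 = 23.3% | +3.3 points |

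The error can go in either direction. Rows 1 and 4 have the same attrition in each group but pool to 20% and 23.3%, because the number of caregivers differs. Rows 4 and 5 have patient attrition of 30% and 20% and pool to the same 23.3%.

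**Linked exits.** If each of 40 patients has a caregiver and the pair leaves together, dc = dp and the error is zero (row 3). If only some patients have caregivers, the rates can differ slightly, because the accompanied patients are a subset.

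**Precision of a separate rate.** The Wilson 95% interval for 12/40 (30%) is 18% to 45%. For 16/80 (20%) it is 13% to 30%, but only if the members of a dyad leave independently.

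**The case against.** The strongest reply is that nothing is lost. Drop-out is counted person by person, so the patient rate can be computed at any time. The adjacent primary outcome, 3.1.3, also records data completeness with reasons. SF-36 completeness is a patient-only figure, and it is arguably a more direct planning input than drop-out. This stands, and it is why the point is minor: the fault lies in how a primary outcome is summarised, not in what is collected.

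A second reply is that the parenthesis in 3.1.2 may only say who is covered, without intending one pooled figure. That is possible. The literal reading is a single proportion, and the same short edit settles it either way.

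A third reply is that the documents do not show that attrition will differ. This also stands. It is tempting to infer that caregivers must leave less often because their only study outcome is the ZBI-12. But Sections 5.0 and 7.0 have intervention-arm caregivers complete the HABC-M at coordinator contacts, which occur at least every two weeks. The in-person plan for 3 and 6 months covers all enrolled subjects and has a remote fallback. Unequal attrition is possible, but neither its direction nor its size can be read from the plan.

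**Conclusion.** The point holds as a minor one. As written, 3.1.2 gives a pooled rate that matches patient attrition only when both groups leave at the same rate, with a caregiver weight that the plan does not fix. Under the assumed rates with 40 caregivers, the gap runs from 10 points below the patient rate to 5 points above it, and it is nil when rates are equal. The algebra needs no assumption beyond some caregivers being enrolled; every rate used is an assumption.

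Two stronger readings are not supported. A reader might infer that the main trial will be under-recruited. Section 11.0 names only effect and variability estimates as inputs to powering that trial and nowhere says that the pooled drop-out rate will set recruitment, so a shortfall cannot be attributed to the plan. A reader might also infer that 3.1.1 mixes refusals with patients who consent and then fail the SF-36 criterion. That sequence is not stated, Section 6.0 does not equate enrollment with randomization (enrolled subjects are assessed and then randomized), and 3.1.1 already records reasons for ineligibility and for non-enrollment.

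No figure stated in the protocol changes.

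**What to change.** Reword 3.1.2 so that drop-out is reported as two rates: patients who drop out over enrolled patients, and caregivers who drop out over enrolled caregivers. The number of caregivers enrolled then no longer affects the patient figure. A combined rate may be kept as a supplement if it is labelled as such.

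The change is one sentence and needs no new data. Its cost is precision: each rate has a smaller denominator and a wider interval, such as the 18% to 45% shown above for 12/40. The narrower pooled interval is not a real gain, because it describes a different quantity and assumes that dyad members leave independently.

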3.2 Secondary Outcome Measures

3.2.1. Quality of Life: This outcome will be obtained from the patient only. Patient health-related QOL will be assessed using the Medical Outcome Study Short Form (SF-36).^{40, 48, 49} This scale has eight components (physical functioning, role-physical, bodily pain, general health, vitality, social functioning, role-emotional, and mental health) that are aggregated into a Physical Component Summary (PCS) and a Mental Component Summary (MCS). Changes that differ by 2 or more points on a scale of 0 to 100 are clinically meaningful.⁴⁹

3.2.2 Physical Performance: Physical performance measures will be obtained from the patient only. Physical recovery will be assessed via the Short Physical Performance Battery (SPPB), a validated objective assessment.⁵⁰ The SPPB yields a performance score of 0-12 (0-4 poor, 5-7 intermediate, 8-12 good). A difference of 1 point indicates significant change in function. The SPPB has been validated in patients with decompensated cirrhosis.^{51, 52} Grip strength will also be obtained to calculate the Liver Frailty Index, <https://liverfrailtyindex.ucsf.edu>, which overlaps with the SPPB.

3.2.3 Depression and Anxiety Symptoms: Depression and anxiety symptoms will be obtained from the patient only. The Patient Health Questionnaire-9 (PHQ-9)^{53, 54} and Generalized Anxiety Disorder Scale (GAD-7)^{55, 56} will be used to measure patient mood and anxiety. The PHQ-9 is a nine-item depression scale with a total score from 0 to 27, and the GAD-7 is a seven-item anxiety scale with a total score from 0 to 21. Both of these scales are derived from the Patient Health Questionnaire, have good internal consistency and test-retest reliability as well as convergent, construct, criterion, procedural and factorial validity for the diagnosis of major depression and general anxiety disorder.

3.2.4 Cognitive Assessment: Cognitive assessment will be obtained from the patient only. 3D CAM and PHES are psychometric measures of hepatic encephalopathy. They are quick, simple paper tests that are easily interpreted. They are components of the gold-standard Psychometric Hepatic Encephalopathy Score.⁵⁷⁻⁶⁰

3.2.5 Caregiver Burden: Caregiver burden will be obtained from the caregiver only. The Zarit Burden Interview-12 (ZBI-12) is a validated instrument that has been utilized in various populations.⁶¹ It has excellent test characteristics when compared with the long form of the ZBI, and it has been used in other studies of cirrhosis.^{4, 62}

3.2.6 Acute Health Care Utilization: Health care utilization will be obtained from the patient only. In addition to patient-reported emergency room and admission data, we will use the Indiana University Health local data warehouse and the larger Indiana Network for Patient Care (INPC) to complement the utilization assessment. INPC is a large health information exchange in Indiana and provides data from all health care systems within the state.⁶³ We will determine the number of emergency room visits and the number of hospitalizations within 6 months of discharge as well as associated diagnoses. As part of this, we will also be tracking admissions specific to COVID-19, due to the large impact the pandemic has had on our healthcare system. We will do that by tracking whether patients are admitted with a COVID-19 diagnosis or die of COVID-19 while enrolled in the study.

3.2.7 CMH Interactions: In patients/caregivers randomized to the Cirrhosis Medical Home, we will record the numbers, timing, and types of interactions with the care coordinator (in-person, phone, video, other forms of communication). We will also record the use of interventions (e.g. care protocols, pharmacologic treatments).

3.2.8 Palliative Care outcomes: Palliative care referrals will be recorded, including presence of a referral order, successful attendance at a palliative care visit, completion of advanced directives, and place of death.

3.3 Other Patient Measures: At baseline, we will measure age, race, gender,

level of education, income, employment, family size and household composition, height, weight, etiology of cirrhosis, liver disease severity (Child-Pugh score,⁶⁴ MELD score⁶⁵), Charlson comorbidity index,⁶⁶ medications, prior health care utilization, and reason for hospital admission.

3.4 Other Caregiver Measures: At baseline, we will measure age, race, gender, location (living with the patient or elsewhere), relationship to patient, and length of time caring for the patient.

The results of this study will establish the feasibility of performing a randomized trial to evaluate the efficacy of the Cirrhosis Medical Home in improving QOL for patients with decompensated cirrhosis. The next step will be to conduct a large-scale efficacy trial.

